5.4.2. SC Administration PF-06863135

Qualified and trained investigator site personnel will administer PF-06863135 to patients by SC injection. Ideally, each injection may be up to 2 mL in volume. However, if the maximum volume allowed per institution's policy is lower, the number of injections may increase to accommodate this difference in volume to ensure the correct final dose is delivered.

Study drug should be administered to the abdomen (with preference given to the lower quadrants when possible). Refer to [Appendix 9](#) for details on administration of multiple injections to the abdomen. Study staff should refer to the IP Manual for specific instructions on the handling and preparation of study drug.

Similar to IV dosing, during monotherapy dose escalation with Q1W SC PF-06863135 only each cycle will be 3 weeks in duration, and each patient will be treated 3 times during each cycle, unless dose delays or interruptions occur (see [Sections 5.5.1](#) and [5.5.2](#)). If patients are enrolled into Q2W SC dosing cohorts during dose escalation, each cycle will be 4 weeks in duration, and each patient will be treated twice during each cycle. On C1D1 for all patients, and on C0D1 for patients receiving a priming dose, PF-06863135 will be administered on an inpatient basis. On all other days, PF-06863135 will be administered on an outpatient basis).

PF-06863135

C1071001

Final Protocol Amendment 9, 28 March 2023

If patients are enrolled into Q2W SC dosing cohorts during dose escalation, each cycle will be 4 weeks in duration, and each patient will be treated twice during each cycle. On C1D1 for all patients, and on C0D1 for patients receiving a priming dose, PF06863135 will be administered on an inpatient basis. On all other days, PF06863135 will be administered on an outpatient basis.

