Details for PF-06863135 injections are provided in the current PF-06863135 IP Manual. The dose level will be assigned by the sponsor (see [Section 5.1 Allocation to Treatment](#)). For monotherapy Part 1, all patients should be weighed within 72 hours prior to Day 1 of each cycle to ensure they did not experience either a weight loss or gain >10% from the prior weight used to calculate the amount of PF-06863135 required for dose preparation. If the patient experienced either a weight loss or gain >10% compared to the prior weight used to calculate the initial dose or dose in the previous cycle, the amount of PF-06863135 required for preparation and administration for the current cycle must be recalculated using this most recent weight obtained. Should the institutional policy be such that the dose is required to be calculated if a patient experiences a weight gain of <10%, this will be allowed. Fixed-dosing approach will be applied in dose-finding for combination and also in all expansion parts of the study (See [Section 1.2.9.4](#)).

Each patient may receive PF-06863135 until disease progression, unacceptable toxicity, withdrawal of consent, patient no longer willing to participate in trial, or study termination. If a patient has received treatment with Q1W PF-06863135 for at least 6 months, and disease assessments have remained stable over at least 2 months, consideration may be given to increasing dose intervals from weekly to every 2 weeks or once per cycle (only CXD1 dosing and activities applicable) after consultation with sponsor. Cycles would remain the same length with any skipped weekly doses noted. If the patient subsequently begins to have increase of disease burden, dose intervals should return to weekly dosing.

For Parts 1C, 1D, 1E and Part 2 dose expansion: PF-06863135 will be administered as described for monotherapy PF-06863135, and each cycle will be 4 weeks in duration. On C1D1 for all patients and C0D1 for patients receiving a priming dose, PF-06863135 will be administered on an inpatient basis. On all other days, PF-06863135 will be administered on an outpatient basis.

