 - The total planned Dexamethasone dose = (planned Dexamethasone dose in mg * 4). *Dexamethasone will be administered at a dose of 40 mg weekly. For subjects older than 75 years or underweight (body mass index [BMI] <18.5), the dexamethasone dose may be administered at a dose of 20 mg weekly. Dexamethasone may be reduced, if necessary, according to Table 10 in the protocol.*

Relative dose intensity at each cycle will be calculated as follows:

- Part 1 (no priming): Cycle length is determined as entered by the site.
 - Dose administered will be the sum of “Calculated Dose Administered” for the cycle.
 - The total planned dose will be the (assigned dose of PF-06863135 *3)
 - If patient discontinues before end of the cycle, the planned dose for the will be based on dosing for number of days on the last cycle based on the dosing page. For example, if patient discontinues after CXD2, the planned dose will be (assigned dose of PF-06863135 *1).
- Part 1.1 Q1W and Part 2A: Cycle length is determined as entered by the site.
 - The total planned dose = (maintenance dose of PF-06863135 * 4).
 - Dose administered will be the sum of “Calculated Dose Administered” for the cycle.
 - If patient discontinues before end of the cycle, the planned dose for the will be based on dosing for number of days on the last cycle based on the dosing page.
- Part 1.1 Q2W: Cycle length is determined as entered by the site.
 - The total planned dose = (maintenance dose of PF-06863135 * 2).
 - Dose administered will be the sum of “Calculated Dose Administered” for the cycle.
 - If patient discontinues before end of the cycle, the planned dose for the will be based on dosing for number of days on the last cycle based on the dosing page.

- Part 1C and 1D: Cycle length is determined as entered by the site.
 - The total planned PF-06863135 dose = (maintenance dose * 4).
 - The total planned Lenalidomide dose = (assigned dose of Lenalidomide in mg * 21).
 - The total planned Pomalidomide dose = (assigned Pomalidomide dose of mg * 21).
 - Dose administered should be the sum of “calculated actual dose” for the cycle.
 - If patient discontinues before end of the cycle, the planned dose for the lenalidomide/pomalidomide will be based on daily dosing for min(number of days on the cycle, 21) as entered in the dosing page .
- Part 1E: Cycle length is determined as entered by the site.
 - The total planned PF-06863135 dose = (maintenance dose * 4).

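### The SAP's relative dose intensity uses fixed planned doses per cycle, so cycles after a protocol-allowed interval change, and Part 1 SC Q2W without priming, read well below 100% with no dose missed

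*SAP*

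**What the plan says.** SAP 6.2.1 sets out the calculation by cycle: "Relative dose intensity at each cycle will be calculated as follows". The planned dose is then fixed by study part:

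- Part 1 (no priming): "The total planned dose will be the (assigned dose of PF-06863135 *3".
- Part 1.1 Q1W and Part 2A: "The total planned dose = (maintenance dose of PF-06863135 * 4".
- Parts 1C, 1D and 1E: "The total planned PF-06863135 dose = (maintenance dose * 4".
- Part 1.1 Q2W: "The total planned dose = (maintenance dose of PF-06863135 * 2".

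The only adjustment is for a patient who stops before the end of a cycle; the Part 1 example is "if patient discontinues after CXD2, the planned dose will be (assigned dose of PF-06863135 *1". Cycle length is taken as the site enters it. SAP 8.2.3.5 lists planned dose, administered dose and percentage of planned dose by subject and cycle, and treats every Part 1 cycle as 3 weeks long.

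Protocol 5.4.2 says that, after at least 6 months of weekly dosing and at least 2 months of stable assessments, "consideration may be given to increasing dose intervals from weekly to every 2 weeks or once per cycle" in consultation with the sponsor. Protocol 5.4.1, Protocol 1.2.9.5 and the Schedules of Activities carry the same option, with cycle length unchanged. For patients who start on Q2W SC dosing during dose escalation, Protocol 5.4.2 states that "each cycle will be 4 weeks in duration, and each patient will be treated twice during each cycle". Schedule of Activities C covers Part 1 SC Q2W without a priming dose.

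**The concern.** The denominator does not follow the schedule that the patient is on. Once the interval is lengthened by agreement with the sponsor, the planned dose stays at three or four weekly doses, and the doses that were deliberately not scheduled count as shortfall. Because cycle length does not change, the site-entered length cannot correct this. The SAP gives Part 1.1 Q2W its own two-dose denominator, which shows that planned dose is meant to track the assigned schedule. That logic is not carried over to patients who move from weekly dosing, nor to Part 1 SC Q2W without priming.

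At stake is the reading of the exposure data. From the percentage alone, an agreed interval change cannot be told apart from doses missed for toxicity or other reasons. The patients concerned are those treated for at least 6 months with stable disease.

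**Working it through.** **Inputs.** The planned-dose multipliers are those of SAP 6.2.1: 3, 4 and 2. Cycle lengths are 21 days for Part 1 and 28 days for the other parts (SAP 8.2.3.5), and 28 days for Q2W cohorts (Protocol 3.1.4 and 5.4.2). The permitted intervals after a change are 14 days or one cycle.

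**Reproducing the SAP's multipliers** as cycle length divided by dosing interval:

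- 21/7 = 3 (Part 1, weekly).
- 28/7 = 4 (Parts 1.1 Q1W, 2A, 1C, 1D, 1E).
- 28/14 = 2 (Part 1.1 Q2W).

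All three agree, so each multiplier is right for the schedule on which the patient starts in those parts.

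**Formula.** The SAP names the two components but does not write the ratio. I take relative dose intensity in a cycle as administered dose divided by planned dose. For a patient who receives every scheduled dose at the assigned level, this is doses scheduled divided by the SAP multiplier.

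**Fully compliant patient, SAP denominator:**

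| Situation | Doses given per cycle | SAP planned doses | Reported |
|---|---|---|---|
| 28-day cycle, after change to Q2W | 2 | 4 | 2/4 = 50% |
| 28-day cycle, after change to once per cycle | 1 | 4 | 1/4 = 25% |
| 21-day cycle, after change to Q2W | 2, then 1, alternating | 3 | 67%, then 33% (average 50%) |
| 21-day cycle, after change to once per cycle | 1 | 3 | 1/3 = 33% |
| Part 1 SC Q2W without priming, 28-day cycle | 2 | 3 | 2/3 = 67% |
| Part 1.1 Q2W from the start, 28-day cycle | 2 | 2 | 100% |

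The alternation arises because strict 14-day dosing from Day 1 falls on Days 1 and 15 of one 21-day cycle and on Day 8 of the next.

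**Over a whole course (illustration only).** The SAP calculates by cycle, so this goes beyond what it specifies. Assume 28-day cycles, 26 weekly doses (6.5 cycles) and then a change, with no dose missed. Twelve months is 12 × 30.4375/28 = 13.04 cycles, of which 6.54 follow the change:

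- Q2W: (26 + 2 × 6.54)/(4 × 13.04) = 74.9%.
- Once per cycle: (26 + 6.54)/(4 × 13.04) = 62.4%.

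At 24 months the same steps give 62.5% and 43.7%.

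**Timing.** SAP section 2 follows the protocol of 06 June 2021 (Amendment 8). The protocol's change log places the Q2W option in Amendment 4, before that version, and once-per-cycle dosing in Amendment 9, after it.

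**The case against.** The strongest reply is that intensity is not compliance. The monotherapy RP2D is a weekly dose (Protocol 3.4). A patient on the same dose every 2 weeks receives half that intensity, so 50% is a true statement about exposure relative to the RP2D. The protocol keeps the weekly schedule as a reference by having skipped weekly doses noted. Replacing the denominator outright would show 100% for a patient who receives a quarter of the weekly amount, and would hide the reduction. This stands as an argument for keeping the original-schedule measure, labelled as such. It does not rescue the SAP as written, which nowhere says that it indexes to the original weekly schedule. Nor can it explain the 67% for Part 1 SC Q2W, whose schedule was never weekly.

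The reach is also limited. The summaries of cumulative dose and of percent of starting dose in SAP 8.2.3.5 do not use the multiplier. No summary table of relative dose intensity is specified. The listings give dosing dates and reasons for dosing changes, so a change of interval can be found by anyone who looks.

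Two stronger readings are tempting. A reader might infer that the formula distorts the basis for the RP2D. Protocol 3.4 rules this out: the dose was selected on Part 1 safety, efficacy, PK and pharmacodynamic data, and relative dose intensity is not among the stated grounds. A reader might also infer from Protocol 1.2.3.2 (response in 63.4% of 41, which is 26 patients, with median DOR 11.6 months) that many responders are affected. The documents give no count of interval changes. The 41 already include patients assigned to Q2W, DOR runs from response and not from first dose, and the change is discretionary.

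**Conclusion.** The gap is real and narrow. Under the SAP's rules, post-change cycles of a patient who misses nothing are reported at 50% or 25% (28-day cycles), or at alternating 67% and 33% or a constant 33% (21-day cycles). Part 1 SC Q2W without priming is reported at 67%. For Q2W this is an omission in the SAP, since the option was already in the protocol that the SAP follows. For once-per-cycle dosing it is an update that Amendment 9 makes necessary.

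The consequence is confined to per-cycle relative dose intensity and the percentage-of-planned-dose listing. DLT evaluability uses the DLT observation period, which ends with Cycle 1, well before the 6 months needed for a change, and its Part 1 rule asks only for one dose. ORR and DOR do not use the formula.

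The percentages rest on reading relative dose intensity as administered over planned, on full dosing at the assigned level, and on strict 14-day spacing for Q2W. How many patients changed interval, and whether anyone was treated on Part 1 SC Q2W without priming, cannot be determined from the documents.

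**What to change.** In SAP 6.2.1:

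1. Define the planned PF-06863135 dose per cycle as the assigned dose times the number of doses scheduled under the interval in force in that cycle, from the date of the agreed change. In 28-day cycles this is 2 for Q2W and 1 for once per cycle. In 21-day cycles it is 2 and 1 alternately for Q2W, and 1 for once per cycle.
2. Add a line for Part 1 SC Q2W without priming with two planned doses per 4-week cycle, and align the Part 1 cycle length in SAP 8.2.3.5.
3. Report the number of patients who changed interval, to which interval and when.
4. Keep intensity against the original weekly schedule as a second, separately labelled measure, so that de-intensification stays visible.

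The cost is SAP wording and a small programming change before database lock. The protocol already asks for skipped weekly doses to be noted, so the information should be at hand. No dosing rule changes.

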6.3. Pharmacokinetics Endpoints

Drug concentrations of PF-06863135 will be measured using validated methods. For patients from Parts 1, 1.1, 1C, and 1D, PK parameters following the Cycle 1 Day 1 dose and Cycle 2 Day 1 dose will be determined separately from the respective concentration-time data using standard noncompartmental methods. Actual sample collection times will be used for the parameter calculations. For PF-06863135, PK parameters including maximum concentration (C_{max}), time to maximum concentration (T_{max}), area under the concentration-time curve over 1 dosing interval (AUC_{τ}), area under the concentration-time curve from time 0 to the last measurable concentration (AUC_{last}), and, if data permit or if considered appropriate, area under the concentration-time curve from time 0 extrapolated to infinity time (AUC_{inf}), terminal elimination half-life ($t_{1/2}$), clearance (CL or CL/F), volume of distribution at steady state (V_{ss}), and accumulation ratio (R_{ac}) will be calculated. PK parameters will be derived from the concentration-time data as follows:

Table 2. PK Parameters

Parameter	Definition	Method of Determination
AUC_{last}	Area under the concentration-time profile from time zero to the time of the last quantifiable concentration	Linear/Log trapezoidal method
AUC_{τ}	Area under the concentration-time	Linear/Log trapezoidal method

Parameter	Definition	Method of Determination
AUC_{inf}	profile from time zero to the time τ , the dosing interval Area under the concentration-time profile from time zero extrapolated to infinite time	$AUC_{(0-t[last])} + (Clast^*/kel)$, where $Clast^*$ is the predicted serum concentration at the last quantifiable time point estimated from the log-linear regression analysis.
C_{min}	Lowest concentration observed during interval	Observed directly from data
C_{max}	Maximum observed concentration	Observed directly from data
T_{max}	Time for C_{max}	Observed directly from data as time of first occurrence
$T_{1/2}$	Terminal elimination half-life	$\log_2(2)/kel$, where kel is the terminal phase rate constant calculated by a linear regression of the log-linear concentration-time curve. Only those data points judged to describe the terminal log-linear decline will be used in the regression.
CL (IV) or CL/F (SC)	Clearance (IV) or apparent clearance (SC)	Dose/ AUC_{inf} for cycle 1; Dose/ AUC_{τ} for cycle 2
V_{ss}	Volume of distribution at steady state	$CL \times MRT$
R_{ac}	Observed accumulation ratio	$AUC_{cycle\ 2,\ \tau}/ AUC_{cycle\ 1,\ \tau}$

For patients enrolled in Part 2A, 2B 2C, and 2D of the study, trough PF-06863135 concentrations will be summarized descriptively by cycle.

Drug concentrations of lenalidomide (Parts 1C and 2C only), and pomalidomide (Parts 1D and 2D only) will be measured using validated methods and summarized by descriptive statistics (n, mean, standard deviation, coefficient of variation, median, minimum, maximum, and geometric mean) according to dosing cohort and time for each part of the study. No PK parameters will be determined for lenalidomide, or pomalidomide.

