41. **Treatment with dexamethasone:** For patients receiving dexamethasone, administer dexamethasone 40 mg orally 60 ± 30 minutes before every dose of PF-06863135 beginning with C0D1; the dose of dexamethasone may be reduced to 20 mg for patients who are older than 75 years of age or who have a body-mass index (the weight in kilograms divided by the square of the height in meters) of less than 18.5. If a dose of PF-06863135 is held or skipped, then dexamethasone should not be administered. Dose adjustments for dexamethasone are provided in [Table 10](#) and, following discussion and agreement between the investigator and sponsor, the dose of dexamethasone may be adjusted for tolerability if needed for a specific patient. For patients receiving dexamethasone premedication, dexamethasone should be discontinued after 6 months unless clinical rationale to continue dexamethasone is provided by investigator and approved by sponsor.

PF-06863135

C1071001

Final Protocol Amendment 9, 28 March 2023

SCHEDULE OF PHARMACOKINETIC, SOLUBLE FACTOR AND CYTOKINE ACTIVITIES B: PART 1.1 AND ANY OTHER PART USING PRIMING DOSE AND MAINTENANCE

The schedule of pharmacokinetic, soluble factor and cytokine activities table provides an overview of the protocol visits and procedures. This schedule of activities is applicable to Part 1.1 and any other parts of the study where a priming dose will be administered. If priming dose and maintenance is selected, this table should be followed.

Grayed out columns should only be performed when Q1W dosing of PF-06863135 being used but not for Q2W dosing.

The investigator may schedule visits (unplanned visits) in addition to those listed in the schedule of activities table in order to conduct evaluations or assessments required to protect the well-being of the patient. See [Appendix 10](#) for alternative measure guidelines due to COVID-19.

| Visit Identifier | Up to 7 days prior to C0D1 | Treatment Period | | | | | | | | | | | | | | | | | | | | EOT | | | |
|---|----------------------------|------------------|---|---------|-------|--------|-----------------------------|----------------|----------------|-------|--------|-----|--------------------------|--------------------------|---------|--------------------------|---|--------------------------|--------------------------|-----------------|--------------------------|-----|---|---|--------------------------|

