| Samples for pomalidomide blood level (Parts 1D and 2D only) ⁵ | | | | | | X | | | | | X | | | X | | | | | | | | | | | |
| Samples for dexamethasone blood level (Parts 1E and 2E only) ⁶ | | X | | | | X | | | | | X | | | X | | | | | | | | | | | |

PF-06863135

C1071001

Final Protocol Amendment 9, 28 March 2023

| Visit Identifier | Up to 7 days prior to C0D1 | Treatment Period | | | | | | | | | | | | | | | | | | EOT | | | | | |
|---|----------------------------|------------------|---|---|---|----|-----------------------------|----------------|----------------|----|----|-----|--------------------------|--------------------------|---|--------------------------|---|--------------------------|--------------------------|-----|--------------------------|-----|--------------------------|----|--------------------------|
| | | Priming Cycle | | | | | Maintenance Dose | | | | | | | | | | | | | | | | | | |
| Study Day | | Cycle 0 (1 wk) | | | | | Cycle 1 (1 Cycle = 4 weeks) | | | | | | | Cycle 2 | | | | | Cycle 3 onwards | | | | | | |
| | | 1 | | 2 | | D1 | | D2 | | D8 | | D15 | | D22 | | D1 | | D8 | | D15 | | D22 | | D1 | |
| | | 0 | 2 | 4 | 8 | 24 | 0 | 2 [*] | 4 [*] | 8 | 24 | 0 | 2 [*] (IV only) | 4 [*] (IV only) | 0 | 2 [*] (IV only) | 0 | 2 [*] (IV only) | 4 [*] (IV only) | 0 | 2 [*] (IV only) | 0 | 2 [*] (IV only) | 0 | 2 [*] (IV only) |
| Soluble BCMA and other factors ⁴ | X | X | X | X | X | X | X | X | X | X | X | X | X | X | X | X | X | X | X | X | X | X | X | X | |

Abbreviations: Anti-drug antibodies = ADA; BCMA = B-cell maturation antigen; D = Day; EOT = end of treatment; neutralizing antibodies =Nab.

* For IV administration, the 2-hour sample should be taken immediately (up to 15 minutes before) before the end of PF-06863135 infusion; if the infusion is longer than 2 hours (or shorter if a 1 hour infusion is tested), the collection time of this sample should be adjusted accordingly for the sample to be collected immediately before the actual end of PF-06863135 infusion. For subcutaneous administration, the 2-hour sample should be taken at 2 hours post-injection ±12 minutes. For Part 2 IV administration lead-in cohort, C2D1 end of infusion sample will be taken at 1 hr immediately (up to 15 minutes) before the end of PF-06863135 infusion. Also for SC administration, 2 and 4 hr samples are not needed other than on Cycle 0 D1 and Cycle 1 D1.

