| 
 To evaluate single dose and multiple dose PK of PF-06863135 given as monotherapy and in combination with lenalidomide or pomalidomide. Additionally, PK of lenalidomide, pomalidomide, and | 
 Pharmacokinetic parameters of PF-06863135: Cycle 1 Day 1 dose and Cycle 2 Day 1 dose maximum concentration (C_{max}), area under the concentration versus time curve from time zero to the last quantifiable time point prior to the next dose (AUC_{last}) and if data permit, |

PF-06863135

C1071001

Final Protocol Amendment 9, 28 March 2023

| | |
|--|--|
| dexamethasone will be evaluated when combined with PF-06863135 (Parts 1C, 1D, and 1E, respectively). | 
clearance (CL or CL/F), volume of distribution at steady state (V_{ss} or V_{ss}/F), and terminal elimination t_{1/2}.
 
 Plasma lenalidomide, pomalidomide, and dexamethasone concentrations at selected time points (Parts 1C, 1D, and 1E, respectively). |
| 
 To evaluate immunogenicity of PF-06863135 as monotherapy and in combination with lenalidomide, pomalidomide, or dexamethasone. To characterize the impact of PF-06863135 as monotherapy and in combination with lenalidomide, pomalidomide, or dexamethasone, on systemic soluble immune factors. | 
 Incidence and titers of anti-drug antibodies (ADA) and neutralizing antibodies (Nab) against PF-06863135. Pre- and post-dose quantification of soluble cytokines in serum. |
| Tertiary/Exploratory Objectives: | Tertiary/Exploratory Endpoints: |

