9.5. Analysis of Pharmacokinetics and Pharmacodynamics

9.5.1. PF-06863135 PK Analysis

The concentrations of PF-06863135 will be summarized by descriptive statistics (n, mean, standard deviation, coefficient of variation, median, minimum maximum, and geometric mean) by dosing cohort, cycle, and nominal time. Individual patient and median profiles of the concentration-time data will be plotted by dosing cohort and cycle using nominal times. Median profiles will be presented on both linear-linear and log-linear scales.

For patients from Parts 1, 1.1, 1C, 1D, and 1E, individual concentration-time data of PF-06863135 following the Cycle 0 Day 1 dose (only for patients receiving priming dose), Cycle 1 Day 1 dose and Cycle 2 Day 1 dose (IV only) will be analyzed separately using non-compartmental analysis to estimate the PK parameters. The PK parameters estimated will include C_{max} , time to maximum concentration (T_{max}), and concentration versus time curve (AUC_{last}). If data permit or if considered appropriate, minimum concentration (C_{min}), terminal elimination half-life ($t_{1/2}$), clearance (CL or CL/F), volume of distribution at steady state (V_{ss} or V_{ss}/F), and accumulation ratio (Rac) will be also estimated for Cycle 1 Day 1 and Cycle 2 Day 1. Actual sample collection times will be used for the parameter calculations. The PK parameters will be summarized descriptively by dosing cohort, and cycle.

For patients enrolled in Parts 2A, 2C, 2D, and 2E of the study, trough PF-06863135 concentrations will be summarized descriptively by cycle.

9.5.2. Lenalidomide, Pomalidomide, and Dexamethasone Pharmacokinetic Analysis (Parts 1C and 2C, Parts 1D and 2D, Parts 1E and 2E as appropriate)

The concentration-time data of lenalidomide, pomalidomide, and dexamethasone will be summarized by descriptive statistics (n, mean, standard deviation, coefficient of variation, median, minimum, maximum, and geometric mean) according to dosing cohort and time for each part of the study.

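### SAP 6.3 plans Cycle 2 Day 1 noncompartmental PK parameters for primed SC patients, whose schedule has no sample between that dose and the next trough

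*SAP*

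**What the plan says.** **SAP 6.3.** Noncompartmental parameters are planned "For patients from Parts 1, 1.1, 1C, and 1D, PK parameters following the Cycle 1 Day 1 dose and Cycle 2 Day 1 dose", without regard to route. Cmax, Tmax, AUCtau and AUClast are listed outright. AUCinf, half-life, clearance, Vss and the accumulation ratio follow only "if data permit or if considered appropriate". SAP Table 2 gives cycle 2 clearance, including apparent SC clearance, as dose divided by AUCtau. It gives the "Observed accumulation ratio" as cycle 2 AUCtau over cycle 1 AUCtau.

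**Protocol 9.5.1.** The same analysis carries a route limit: "Cycle 1 Day 1 dose and Cycle 2 Day 1 dose (IV only) will be analyzed separately".

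**PK Schedule B.** "This schedule of activities is applicable to Part 1.1 and any other parts of the study where a priming dose will be administered". Protocol 3.4 and 3.1.1.4 (Table 1) apply priming to Part 1.1 and to Parts 1C and 1D. In Cycle 2 the 2 h and 4 h columns are headed IV only, and the footnote adds: "Also for SC administration, 2 and 4 hr samples are not needed other than on Cycle 0 D1 and Cycle 1 D1".

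**Objective.** Both documents have the secondary PK objective "To evaluate single dose and multiple dose PK of PF-06863135 given as monotherapy" and in combination. Their endpoint tables (Protocol Summary and 2.1; SAP 2.2.1) list C2D1 Cmax and AUClast with no route limit.

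**The concern.** The SAP asks for a peak, a time of peak and an area over a dosing interval in which these patients are not sampled. SC absorption is slow, so the peak lies days after the dose.

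Two quantifiable troughs are still enough to produce numbers. Cmax becomes the larger trough, Tmax falls on an interval boundary, and AUCtau is the area under one line joining two troughs. Under SAP 8.2.5.1 these would enter the summary tables and the dose-normalised plots as multiple-dose PK of the priming-plus-maintenance regimen, the regimen that protocol 3.4 carries forward.

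SAP Section 2 states that the SAP supersedes the protocol's statistical considerations and will identify substantial differences. The loss of the IV limit is not identified.

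**Working it through.** **Step 1. Count scheduled PK samples after the C2D1 dose and before the next dose.**

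| Cohort and schedule | Sample times (h) | Inside the interval |
|---|---|---|
| Primed SC, weekly (B) | 0, 168 | 0 |
| Primed SC, every 2 weeks (B; Day 8 skipped) | 0, 336 | 0 |
| Primed IV, weekly (B) | 0, 2, 4, 168 | 2 |
| Unprimed SC, weekly (A or C) | 0, 72, 168 | 1 |

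Schedule of Activities B still has a footnote pointing to C1D4 and C2D4 assessments. PK Schedule B has no such columns, and the Amendment 7 log records that those visits were removed. Samples triggered by suspected CRS or by serious or unexpected AEs do not make a planned profile.

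**Step 2. Count patients.** Protocol 1.2.3.1, cutoff 22 June 2022: 20 (Part 1.1) + 4 (1C) + 9 (1D) = 33. This is enrolment, so it is an upper bound. Schedule B lost its C2D4 visit with Amendment 7 (15 January 2021). That amendment already cites preliminary data on priming, so some Part 1.1 patients were dosed earlier and may have a 72 h sample.

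**Step 3. Illustrate the bias.** The inputs are:
- Doses: 44 mg priming, then 76 mg from day 7 (protocol 3.4). C2D1 is day 35.
- Half-life: 3.5 to 10 days. The documents give 3.5 (1.2.9.1), 4-8 (1.2.9.5) and 10 (1.2.3).
- Absorption rate: in neither document. Two assumed ranges are used: 0.22-0.5/day, and absorption half-lives of 0.5-3 days.
- Model: one compartment, first-order absorption. Each dose adds D·ka/(ka−ke)·(e^(−ke·t) − e^(−ka·t)), with F/V set to 1.

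Check against the plan's own figure: at 3.5 days with weekly dosing, accumulation is 1/(1 − e^(−ln2·7/3.5)) = 1/(1 − 0.25) = 1.33, as in protocol 1.2.9.1.

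Worked case, weekly, half-life 3.5 days, ka 0.5/day:
- Troughs are 37.94 and 38.01; the true peak is 65.28. Cmax ratio = 38.01/65.28 = 0.58.
- Two-trough AUCtau = 7 × (37.94 + 38.01)/2 = 265.8; the true value is 383.4. Ratio = 0.69.
- CL/F = dose/AUCtau, so it is overstated by 383.4/265.8 = 1.44, or 44%.

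Ranges over the grid:

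| | Cmax, % of true | AUCtau, % of true | CL/F |
|---|---|---|---|
| Weekly, ka 0.22-0.5/day | 58-93 | 69-93 | 7-44% too high |
| Weekly, absorption half-life 0.5-3 d | 38-92 | 54-93 | 8-86% too high |
| Every 2 weeks, ka 0.22-0.5/day | 18-72 | 30-79 | 1.3-3.3 times true |

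With ka 0.22-0.5/day, the modelled true Tmax is about 2 to 5 days after the dose. With the second absorption range and weekly dosing, the accumulation ratio comes out at 0.72-2.57 against a true 1.20-2.49.

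**Step 4. Add the 72 h sample (weekly dosing).** Over both absorption ranges, Cmax recovers to 83-100% and AUCtau to 83-98% of true. That one sample separates usable from unusable data.

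**The case against.** The strongest reply is that the SAP already has safeguards. CL/F and the accumulation ratio are conditional. SAP 8.2.5.1 summarises a parameter only where the data allow its calculation. SAP 7.1.3 codes values that cannot be derived as NC and requires at least 3 evaluable values. That two troughs would in fact be reported as a Cmax is a prediction, not something the SAP states. This stands for CL/F and the accumulation ratio. It does not settle Cmax or AUCtau: both can be derived from two quantifiable troughs, and the SAP sets no minimum number of samples.

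A reader might infer that the multiple-dose objective cannot be met at all. The documents do not support that. IV patients (23 enrolled) have C2D1 post-dose samples, and unprimed SC patients (30 enrolled in Part 1 SC) have the 72 h draw. Primed patients still give troughs, and population PK is foreseen.

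A reader might also want the protocol's IV-only limit restored for everyone. That would discard C2D1 results from unprimed SC patients which Step 4 shows to be usable.

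Finally, this is a descriptive secondary endpoint in a non-inferential plan. The monotherapy RP2D is already selected and enrolment is complete. That limits the consequence but does not remove the contradiction.

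**Conclusion.** The point holds, narrowly. For primed SC patients on the current Schedule B, the SAP plans C2D1 Cmax, Tmax, AUCtau and AUClast without the samples to support them, and departs from protocol 9.5.1 without identifying it. This follows from the text alone and needs no model.

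The direction of bias is the same in every modelled case: Cmax and AUCtau too low, CL/F too high. The percentages depend on an assumed absorption rate and are illustrative only. The error in the accumulation ratio runs from about −40% to +3%.

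At most 33 patients are affected, fewer if some have a C2D4 sample from before Amendment 7 or did not reach C2D1. The monotherapy part of the multiple-dose objective keeps IV and unprimed SC data. The lenalidomide and pomalidomide part rests on primed SC cohorts (Parts 1C and 1D), so it is the part most exposed. No efficacy, safety or dose decision in the documents is shown to depend on these values.

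**What to change.** - In SAP 6.3 and 8.2.5.1, and in the endpoint tables of both documents, derive C2D1 noncompartmental parameters only for patients with at least one post-dose sample within the C2D1 dosing interval: IV patients, and SC patients with the 72 h C2D4 sample.
- Identify this in the SAP as a difference from protocol 9.5.1, or align 9.5.1 with it.
- For primed SC patients without such a sample, do not report C2D1 Cmax, Tmax, AUCtau, AUClast, CL/F or an AUC-based accumulation ratio. Report the C2D1 and next pre-dose trough concentrations and a trough accumulation ratio. Take exposure from the population PK model foreseen in protocol 9.5.3, if it is performed.

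The cost is wording only, with no new samples or visits. The downside is fewer noncompartmental parameters in the CSR for the primed SC cohorts. Because protocol 9.5.3 makes the population model optional, those cohorts would have troughs alone if it is not run.
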